## Methods and Procedures

This study will involve two sessions, completed approximately one week apart. The sessions will be identical except that one session will involve active neurostimulation and the other will involve sham stimulation. We will use a double-blind, cross-over procedure so that across participants the sham session will be equally likely to have occurred first or second and so that both participants and experimenters will be unaware of which session includes the active simulation.

After providing written informed consent, participants will complete two short self-report measures of paranoid thinking:

- 1) The Paranoia Scale (PS; Fenigstein & Venable, 1992) is a self-report measure designed to assess sub-clinical paranoid thought. Scores range from 20-100 with higher scores indicating higher levels of sub-clinical paranoia. 3 minutes.
- 2) The State Social Paranoia Scale (SSPS; Freeman et al., 2007). The SSPS is a psychometrically sound 20-item self-report measure assessing current levels of paranoid, positive, and neutral thinking about others. Participants read each statement and rate how much they agree on a scale from 1-5. 3 minutes

Participants will then begin the neurostimulation portion of the session, which will last for 20 minutes. The participant will be set up with the tDCS material that will start real or sham stimulation, and participants will be informed that they may read or otherwise entertain themselves during this portion of the study. The two electrodes of the tDCS will be placed over the left and right ventrolateral prefrontal cortex. For active stimulation the electrical current will be initially increased in a ramp-like fashion over several seconds (5 seconds) until reaching 1.5mA, and stimulation will be maintained for 20 minutes until it ramps down (5 seconds). For sham stimulation, the electrical current will be increased in a ramp-like fashion over several seconds (5 seconds) until reaching 1.5mA to mimic the sensation present during the first 5 seconds of real stimulation, and then stimulation will be stopped without the participant knowing. The total duration of the sham tDCS will be identical to the active condition in order to appropriately blind the procedure.

Following the neurostimulation portion, the participant will be asked to sit quietly for 30 minutes. After that time has elapsed, the participant will complete the following behavioral measures in a random order:

- 1) Trustworthiness Task (Adolphs, Tranel, & Damasio, 1998). In this task, participants rate 42 faces for trustworthiness on a scale from -3 to 3. Faces are presented in grayscale and represent ethnically diverse males and females. 4 minutes.
- 2) Emotion Recognition 40 (ER-40; Kohler, Turner, Bilker, Brinsinger, Siegel, Kanes... Gur, 2003). The ER-40 is a standardized, computer administered measure of facial affect recognition ability. It includes 40 color photographs of faces expressing 4 basic emotions (i.e. happiness, sadness, anger or fear) and neutral expressions. Participants view one face at a time and are asked to choose the correct emotion for each face. 3 minutes
- 3) Ambiguous Intentions and Hostility Questionnaire (AIHQ) (Combs, Penn, Wicher, & Waldheter, 2007). The AIHQ is a paper-and-pencil measure designed to evaluate hostile

social cognitive biases. It is comprised of 15 hypothetical situations which reflect causes that are either ambiguous, intentional, or accidental (e.g. ambiguous: "you walk past a group of teenagers and you hear them start to laugh"). Participants are asked to read each situation, imagine that it has happened to them, and to write a reason why it happened. They are also asked to record how they would respond to each situation. 6 minutes.

- 4) Intentionality Bias Task (IBT; Peyroux, Strickland, Tapiero, & Franck, 2014). This measure assesses the tendency to attribute intentionality to the actions of others. Participants read 36 very brief descriptions of actions (e.g. "Mark slipped on the walkway") and then rate whether the action was intentional or unintentional. 5 minutes.
- 5) Achievement and Relationships Attribution Task (ARAT; fornells-Ambrojo & Garety, 2009). The ARAT consists of 12 scenarios that describe everyday events (e.g., a first date that does not go well), and participants are asked to answer a question about the outcome of the event. Responses are rated for the type of attribution that is made. 10 minutes.
- 6) The Beck Depression Inventory-2 (BDI-2; Beck et al., 1996) is a 21-item self-report scale that assesses the severity of depressive symptoms. The BDI-2 has excellent psychometric properties and is used extensively in psychological research. Higher scores indicate more severe depression. 3 minutes.
- 7) The Rosenberg Self-Esteem Scale (RSES; Rosenberg, 1965) is a 10-item self-report measure used to assess level of self-esteem. Responses are made using a Likert scale from 1-4, and higher scores indicate higher levels of self-esteem. The RSES shows good internal consistency ( $\alpha=.92$ ) and convergent validity. 3 minutes.
- 8) Brief Core Schema Scales (BCSS; Fowler et al., 2006). The BCSS is a short self-report measure of positive and negative evaluations of the self and others. It has good psychometric properties and has more independence from mood state than other similar measures. 3 minutes.
- 9) The Depression Anxiety Stress Scales (DASS; Lovibond & Lovibond, 1995) is a 21-item self-report measure of the related negative emotion states of depression, anxiety, and tension/stress. 3 minutes
- 10) PS & SSPS - see descriptions above.

At the end of the session, we will ask participants to report which session they believed they just received. This will allow us to assess the success of our blinding procedure.

A repeated-measures ANOVAs will be used to compare indices of paranoia and related constructs between stimulation conditions.

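### Does the plan need to say whether a participant's random order of post-stimulation measures is reused in the second session?

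*Combined protocol and SAP*

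**What the plan says.** All the relevant text is in Methods and Procedures.

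- After stimulation there is a fixed wait: "Following the neurostimulation portion, the participant will be asked to sit quietly for 30 minutes".
- The measures are then taken: "After that time has elapsed, the participant will complete the following behavioral measures in a random order". Ten numbered entries follow. The last is a repeat of the Paranoia Scale (PS) and the State Social Paranoia Scale (SSPS), both also given before stimulation.
- On how the two sessions compare: "The sessions will be identical except that one session will involve active neurostimulation and the other will involve sham stimulation".
- On analysis: "A repeated-measures ANOVAs will be used to compare indices of paranoia and related constructs between stimulation conditions". No term for order, position or time since stimulation is named.

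Nowhere is it stated whether the random order belongs to the participant, and so is used twice, or to the session, and so is drawn twice.

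**The concern.** A cross-over gains its precision from comparing each person with himself or herself under like conditions. If the order is redrawn, a participant's active and sham scores on one measure are taken at different times after stimulation and after different tasks. The analysis sentence names nothing that would absorb such variation, so it would stay in the error term.

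Some measures could plausibly be sensitive to this. The SSPS is described as "assessing current levels of paranoid, positive, and neutral thinking about others", and the Ambiguous Intentions and Hostility Questionnaire (AIHQ) has participants imagine unpleasant social events happening to them. Under a redraw, the AIHQ would precede the PS/SSPS entry in one session and follow it in the other for half of participants. At stake would be precision, not the direction of the result.

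**Working it through.** The plan states no timing gap, sample size or power figure, so there is nothing of its own to reproduce. The check asks how large the gap could be and what it could cost.

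**Inputs (durations in Methods and Procedures, minutes).** Trustworthiness Task 4, ER-40 3, AIHQ 6, Intentionality Bias Task 5, Achievement and Relationships Attribution Task (ARAT) 10, BDI-2 3, RSES 3, BCSS 3, DASS 3, PS and SSPS 3 + 3 = 6, taken as one entry. Total: 4+3+6+5+10+3+3+3+3+6 = 46. The 30-minute wait is the same in both sessions and cancels.

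**If the order is reused.** Every between-session gap due to order is 0.

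**If the order is redrawn independently.** A measure's start time is the sum of the durations d of the entries that come before it. Over a uniformly random order of ten entries, the variance of the start time is

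sum(d²)/4 + [(sum d)² − sum(d²)]/12,

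with sums over the other nine entries. The SD of the between-session gap is the square root of twice this.

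- PS/SSPS: sum d = 40, sum d² = 222. Variance = 55.5 + 1378/12 = 170.3; SD of start 13.05; SD of gap √340.7 = 18.46.
- ARAT: sum d = 36, sum d² = 158. Variance = 39.5 + 1138/12 = 134.3; SD of gap 16.39.
- Any 3-minute entry: sum d = 43, sum d² = 249. Variance = 62.25 + 1600/12 = 195.6; SD of gap 19.78.

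Mean absolute gaps come from the exact start-time distribution, obtained by counting the subsets of other entries that can precede each one; a simulation of 200,000 pairs of orders agreed.

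| Entry | Mean absolute gap (min) |
|---|---|
| ARAT | 13.4 |
| AIHQ, PS/SSPS | 15.1 |
| Intentionality Bias Task | 15.4 |
| Trustworthiness Task | 15.8 |
| 3-minute entries | 16.1 |

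Treating PS and SSPS as two separate entries gives 13.2 to 16.0. Shuffling only the five tasks at the head of the list would give 7.4 to 10.3, although the text places all ten entries under the random-order sentence.

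**Bias.** The signed gap has mean 0, because neither order depends on which session is active. Chance imbalance in mean PS/SSPS timing is 1.96 × 18.46/√n. The supplied text gives no n; for an assumed 20 it is ±8.1 minutes and for an assumed 100 it is ±3.6. This is sampling variation that already enters the within-person error, so the test remains valid.

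**Precision (assumption: linear drift common to both sessions).** The documents give no drift figure, so two scalings are shown.

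- Drift of k SDs of the within-person difference over the 40-minute range of PS/SSPS start times: added variance (k × 18.46/40)² = 0.213k². This is 1.3% at k = 0.25, 5.3% at k = 0.5 and 21% at k = 1.
- Drift of k single-session within-person SDs over 46 minutes, 3-minute measure, independent session errors: (19.78/46)²/2 × k² = 0.0925k². This is 0.4% at k = 0.2, 2.3% at k = 0.5 and 9.2% at k = 1.

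The scalings differ mainly in unit: one SD of the difference is √2, about 1.4, single-session SDs. With no drift, both give 0.

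**What reusing the order could not remove.** If the quantity that changes with time is a fading stimulation effect, it is present only in the active session. The variance it adds depends on when the active measure is taken, and that has the same distribution whether the order is reused or redrawn.

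**The case for a change.** The best case for acting is that the gap in the text is real. Two experimenters could follow the section faithfully and do different things, because running the same random-order procedure afresh each time can also be called an identical session. Under a redraw, the PS/SSPS start times differ by at least 20 minutes in about 32% of participants, and the number of AIHQ and ARAT tasks preceding PS/SSPS differs for two thirds. The text does not say the order is recorded, so later adjustment might not be possible. The remedy would be a sentence or two and an order list.

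The ambiguity and the timing figures stand. What does not stand is the step from minutes to harm. The discordance figures describe task orderings, not changes in score, and nothing in the documents says that the AIHQ or ARAT shifts the SSPS. The 21% figure needs drift of a full SD of the active-sham difference over 40 minutes. Nor is the argument equally relevant to every measure: the BCSS, for instance, is described as less dependent on mood state than its alternatives. Reuse also has a cost, since participants may notice the repeated order.

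**Conclusion.** No change is needed. This is missing detail that those running the study can settle sensibly, and the sentence on identical sessions already points to one answer, under which every gap is zero. Under the other answer the comparison remains unbiased and valid, because the order is drawn independently of condition. A loss would require both a redraw and scores that depend on elapsed time or preceding task; the documents establish neither. Its size is nil without drift and about 0.4% to 5% of the variance under modest to moderate assumed drift (0.2 to 0.5 SD across the two scalings). Random ordering already guards against a consistent position effect, so reuse versus redraw is a choice between two acceptable procedures. Writing the rule down would be optional tidying, and would leave untouched any variation from a fading stimulation effect.

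This rests on the listed durations, on a uniformly random order over the ten entries, and on drift that is linear and common to both sessions. Evidence of steep drift, near a full SD over the battery, would change the size of the loss but not the absence of bias.

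### The cross-over analysis names only the active-versus-sham contrast, so any shift between sessions would inflate the error term or, with unequal orders, bias the estimate

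*Combined protocol and SAP*

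**What the plan says.** All references are to the combined protocol and SAP, Methods and Procedures.

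- **Design.** The trial is a within-participant cross-over: "This study will involve two sessions, completed approximately one week apart". Nothing but the stimulation is meant to differ between the two visits, and the same instruments are used at both; the plan's words are "The sessions will be identical except that one session will involve active neurostimulation and the other will involve sham stimulation".
- **Order.** The plan intends that "across participants the sham session will be equally likely to have occurred first or second". It does not say whether an exact 1:1 split is enforced or only expected.
- **Measures.** Before stimulation, "participants will complete two short self-report measures of paranoid thinking" (PS and SSPS). After stimulation and a rest, "the participant will complete the following behavioral measures in a random order". Items 1 to 9 of that list are given only after stimulation. Item 10 repeats the two paranoia scales: "PS & SSPS - see descriptions above".
- **Analysis.** The section closes with "A repeated-measures ANOVAs will be used to compare indices of paranoia and related constructs between stimulation conditions".

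The only other analysis mentioned is the check on blinding. The text does not say how the pre-stimulation PS and SSPS scores enter the model. An opening part of the document was not available, so these statements cover the available text only.

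**The concern.** The closing sentence gives a contrast and a family of tests but not the model. With two conditions, a repeated-measures ANOVA whose only factor is condition is a paired t test. That test has no place for a difference between the first and second session.

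The documents show no evidence that scores shift between sessions. A shift is possible because the same instruments are repeated about a week later. One of them, the ER-40, has right answers ("Participants view one face at a time and are asked to choose the correct emotion for each face"), so practice could matter. The point bears most on the nine instruments given only after stimulation. For PS and SSPS, the pre-stimulation scores could absorb a shift common to pre and post, but no such use is stated.

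If there is a shift, the bare comparison discards information that the trial already holds, namely who had which order. If the analysed orders are unequal, through chance allocation or dropout, part of the shift is reported as an effect of stimulation.

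**Working it through.** The plan states no sample size, SD, effect size or power, so there is no figure of its own to reproduce. The check is algebra plus simulation.

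**Assumptions, none from the documents.** p = session shift ÷ SD of the within-participant difference within an order, from 0 to 1.0. N = 30, with splits 15/15, 18/12 and 20/10. No carry-over. Two-sided 5% tests.

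**Model.** For each participant, active minus sham is d = τ + shift + error if active comes second, and d = τ − shift + error if active comes first.

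**Equal orders.** The shifts cancel in the mean of d, so there is no bias and the true sampling SD is unchanged. The ±shift pattern still counts as error, so the estimated error variance is multiplied by 1 + p². Hence, in large samples:

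- interval width ratio = √(1 + p²)
- type I error = 2 × [1 − Φ(1.96 × √(1 + p²))]
- power = Φ(2.802 − 1.96 × √(1 + p²)), set to 80% at p = 0

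| p | Width ratio | Type I error | Power |
|---|---|---|---|
| 0 | 1.00 | 5.0% | 80% |
| 0.2 | √1.04 = 1.02 | 4.6% | 79% |
| 0.3 | √1.09 = 1.04 | 4.1% | 78% |
| 0.5 | √1.25 = 1.12 | 2.8% | 73% |
| 1.0 | √2 = 1.41 | 0.6% | 51% |

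Simulation at 15/15 (200,000 runs per cell, true effect 0.529 SD) agrees. Power without a session term is 0.77, 0.72 and 0.50 at p = 0.3, 0.5 and 1.0. With the term it is 0.80 throughout.

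**Unequal orders.** Given the realised split, bias = shift × (n1 − n2)/N. For 18/12 this is 6/30 = 0.20 × shift; for 20/10 it is 10/30 = 0.33 × shift. Simulated type I error with no true effect:

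| Split | Analysis | p = 0.3 | p = 0.5 | p = 1.0 |
|---|---|---|---|---|
| 18/12 | No session term | 5.1% | 5.3% | 4.6% |
| 18/12 | Session term | 5.0% | 5.0% | 5.1% |
| 18/12 | Condition-by-order ANOVA, sequential or Type II | 6.1% | 8.3% | 18.5% |
| 20/10 | No session term | 7.1% | 10.1% | 17.3% |
| 20/10 | Session term | 5.0% | 5.0% | 5.0% |
| 20/10 | Condition-by-order ANOVA, sequential or Type II | 8.2% | 14.2% | 42.0% |

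The sequential and Type II rows are worst because those tests keep the biased raw mean while removing the shift from the error term. At 18/12 without a session term, bias and the inflated standard error roughly offset under the null. They do not offset when there is a true effect: at p = 0.5, power is 0.87 or 0.53 according to the sign of the shift, against 0.78 with the term.

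**How likely are such splits?** If order were a coin flip with N = 30, a split of 18/12 or worse has probability 0.36, and 20/10 or worse 0.10. Averaged over coin-flip order (N = 20, 30 and 60), the bare test keeps type I error at 5.0% to 5.2%. Sequential or Type II tests give about 6%, 8% and 16% at p = 0.3, 0.5 and 1.0.

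**Second check, assumed N = 40.** At 20/20, power falls from 79% to 77%, 72% and 49% at p = 0.25, 0.5 and 1.0. At 24/16, type I error is 5.5%, 6.1% and 6.7%; at 28/12 it is 8.3%, 17.7% and 41.9%. With a session term it is 4.8% to 5.2% in every scenario.

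**The case against.** The sentence is incomplete rather than wrong. A repeated-measures ANOVA can carry order as a between-participant factor, and nothing in the text forbids it. The paired-comparison results follow only if naming one contrast means fitting one factor.

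The harm is also conditional. It needs a shift that nothing in the documents demonstrates, and at p = 0.2 to 0.3 with equal orders the loss is 1 to 2 points of power. The wording on order reads most naturally as counterbalancing. On that reading there is no bias before dropout, and the test errs on the conservative side. Even with coin-flip order, the bare test holds its overall type I error. The largest error rates belong to a choice of sums of squares that the plan does not make. Finally, a mixed model is not the only remedy, and for PS and SSPS a pre/post analysis might already deal with a shared shift.

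All of this is fair, and it limits the point to a specification gap with conditional consequences. It does not remove it. Counterbalancing protects the point estimate but does not restore the lost power, and dropout can unbalance the analysed orders. The open wording allows tests that behave quite differently on the same data. The nine post-only instruments have no pre-stimulation score within the session to fall back on.

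**Conclusion.** The concern holds. In the available text, the outcome analysis leaves the cross-over model terms unspecified, and followed literally it is a paired comparison that ignores session.

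The consequence depends on the unknown shift. It is nil with no shift and small at 0.2 to 0.3 SD with equal orders. At 0.5 SD intervals are 12% wider and power is 73% instead of 80%; at 1.0 SD they are 41% wider and power is 51%. With unequal analysed orders, the estimate carries a bias of shift × (n1 − n2)/N given that split, and rejection can rise or fall. There is no systematic bias averaged over chance allocation. The sizes rest on assumed values of N, split and shift, and on no carry-over. The direction of the result does not depend on those values. It should be fixed, because the remedy uses the order the trial already assigns and costs almost nothing.

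**What to change.** Replace the closing sentence with wording such as:

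> Each outcome will be analysed with a linear mixed model with fixed effects for stimulation condition, session (1 or 2) and order (active-first or sham-first), and a random participant intercept. The condition effect is the test of interest, with Kenward-Roger degrees of freedom.

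Also state how the order split is controlled, and whether and how the pre-stimulation PS and SSPS scores are used.

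If the sponsor prefers a repeated-measures ANOVA, it should include condition, order and condition-by-order, because in this design the interaction carries the session effect. An order main effect alone leaves the condition test unchanged. The ANOVA matches the mixed model's condition test only with complete data and Type III (unweighted, sum-to-zero coded) sums of squares. In 450 simulated complete data sets the estimates agreed to 1e-14 and the standard errors to 5e-6. Sequential or Type II sums of squares must not be used when orders are unequal. If a participant misses a session, the mixed model keeps the observed session and the ANOVA drops the participant.

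**Cost.** One sentence of wording, with no added visits or participants. With equal orders it takes one residual degree of freedom (simulated power 0.80 either way at p = 0, N = 30). With unequal orders and no shift, the standard error grows by √[N(1/n1 + 1/n2)]/2:

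- 18/12: √[30 × (1/18 + 1/12)]/2 = 1.02, power 0.78 against 0.80
- 20/10: √[30 × (1/20 + 1/10)]/2 = 1.06, power 0.75 against 0.80

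None of this removes carry-over that differs between the two orders.

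### The analysis sentence names no primary outcome, significance level or multiplicity rule for a battery of eleven post-stimulation instruments

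*Combined protocol and SAP*

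**What the plan says.** The last line of Methods and Procedures is the whole analysis plan in the text available: "A repeated-measures ANOVAs will be used to compare indices of paranoia and related constructs between stimulation conditions".

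The data come from a two-session cross-over of active and sham stimulation. The section says that "The sessions will be identical except that one session will involve active neurostimulation and the other will involve sham stimulation", and that "across participants the sham session will be equally likely to have occurred first or second". Each index therefore yields one within-participant contrast.

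Before stimulation, "participants will complete two short self-report measures of paranoid thinking": the Paranoia Scale (PS) and the State Social Paranoia Scale (SSPS). Thirty minutes after stimulation ends, "the participant will complete the following behavioral measures in a random order". That list has ten numbered entries, the tenth being "PS & SSPS - see descriptions above". Because the order is random, list position implies no ranking of outcomes.

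The section gives no significance level. The alpha of .92 quoted for the Rosenberg scale is internal consistency.

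**The concern.** The sentence commits to more than one comparison and leaves four things open:

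- which indices will be compared;
- which of them decides the paranoia question;
- whether the depression, self-esteem and distress scales (BDI-2, RSES, DASS) are outcomes or descriptive measures;
- whether the pre-stimulation PS and SSPS scores enter the analysis.

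The natural reading is a series of ANOVAs, any one of which could be reported as a stimulation effect if nominally significant. Nothing in the section fixes the deciding index before results are seen, and nothing says how to read a mixed pattern, such as a change on one task and none on either paranoia scale. A positive report could then carry an error rate well above the level it appears to have.

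**Working it through.** The section gives no sample size, power or significance level, so there is no figure of the plan's own to reproduce.

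**Count of instruments (from the numbered list).** Entries 1 to 9 are the Trustworthiness Task, ER-40, AIHQ, IBT, ARAT, BDI-2, RSES, BCSS and DASS. Entry 10 holds PS and SSPS. Total: 9 + 2 = 11.

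One index per instrument is not a generous count for the full battery. The SSPS is described as "assessing current levels of paranoid, positive, and neutral thinking about others", the BCSS covers self and others both positively and negatively, and the DASS covers three emotion states.

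**Assumptions (not in the documents).** Two-sided 0.05 for each test; no true effect; equal correlation r between all test statistics, that is, between the active-minus-sham differences; and the number of tests k.

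**Formulas.**

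- Independent tests: 1 − 0.95^k. For k = 11: 1 − 0.95^11 = 0.431.
- Correlated tests: 1 − ∫ φ(u) [Φ((c − √r·u)/√(1−r)) − Φ((−c − √r·u)/√(1−r))]^k du, with c = 1.96, by numerical integration.

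**Chance of at least one false positive.**

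| Tests counted | r = 0 | r = 0.5 | r = 0.7 | r = 0.9 |
|---|---|---|---|---|
| 2 (PS and SSPS only) | 9.8% | 9.1% | 8.4% | 7.0% |
| 4 | 18.5% | 15.6% | 13.0% | 9.4% |
| 8 (without BDI-2, RSES, DASS) | 34% | 25% | 19% | 12% |
| 11 (one per instrument) | 43% | 30% | 22% | 13% |
| 20 (assumed, with subscales) | 64% | 42% | 29% | 16% |

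For k = 11 the figure falls further, to 10% at r = 0.95 and 7% at r = 0.99, and approaches 5% as r nears 1. The 13% is therefore not a floor.

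**Check with t-tests.** With two conditions, a repeated-measures ANOVA with condition as its only factor is a paired t-test. Simulating eleven of them (40,000 replicates, assumed sample sizes) gives, at r = 0, 0.5 and 0.9:

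- n = 20: 43.1%, 31.1%, 13.5%
- n = 40: 43.0%, 30.7%, 13.4%

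The normal approximation is adequate here.

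**The case against.** The strongest objection is that the document was only partly available. Aims or a named primary outcome may sit ahead of Methods and Procedures. That stands: the omission is shown for this section and not for the whole plan, and confidence is medium for that reason.

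Second, the sentence does not say that all eleven instruments will be tested, and 43% also needs full independence. The battery has evident overlap: BDI-2 and DASS both cover depression, and PS and SSPS both cover paranoia. This stands as a limit on the size. It does not remove the problem, because two tests already exceed 5%, and the sentence promises more than the paranoia indices.

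Third, the wording mixes singular and plural, so one model with measure as a factor is not excluded. The eleven-test arithmetic would not describe such a model. It would still leave no index that decides the paranoia question.

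Fourth, the section makes no confirmatory claim, and the study may be meant as exploratory. That would be a sufficient answer if the plan said so.

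Finally, nothing in the section ranks SSPS above PS or the behavioural tasks. SSPS also falls at a random point in a battery whose stated times add up to 46 minutes. The choice of primary is therefore a suggestion only.

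**Conclusion.** The concern holds for the section available. It commits to several unlisted comparisons and fixes no deciding index, level or error control. With one index per instrument, the chance of any false positive is 43%, 30% or 13% at correlations 0, 0.5 and 0.9. Only the count of eleven comes from the document; the 0.05 level, the equal correlations and the number of indices are assumptions. On the narrowest reading, two paranoia scales, the range is 9.8% to 7.0%. The sponsor should correct this before unblinding. If a primary outcome is named earlier in the document, it need only be carried into the analysis paragraph, with a level and a rule for the other indices.

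**What to change.** Before unblinding, rewrite the analysis paragraph as follows.

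1. **Primary.** Name one outcome and rest the paranoia conclusion on it alone at two-sided 0.05. A reasonable choice, for the sponsor to confirm, is the post-stimulation SSPS paranoid-thinking score, since SSPS is the only paranoia measure described as capturing current levels.
   - Compare active with sham in a model with condition, period (first or second session), a participant effect, and that session's pre-stimulation SSPS paranoid score.
   - With a fixed participant effect, this equals regressing each participant's active-minus-sham post score on order (coded −1/+1) and on the active-minus-sham pre score; the intercept is the stimulation effect. On one simulated data set (30 participants, assumed), both forms gave estimate 0.648, standard error 0.247, t = 2.62 and 27 residual degrees of freedom.
   - The covariate needs the pre-stimulation SSPS at both sessions, which the identical-sessions statement implies. If it is taken once, the participant effect absorbs it and it is left out.
   - The period term and covariate serve the precision of the primary test. They are not part of the multiplicity control.
2. **Secondary.** Name one index for each other instrument meant to support a claim, and apply Holm's procedure at 0.05 across that set.
3. **Exploratory.** Label every other index so. If the whole battery is exploratory, say that and draw no confirmatory conclusion.

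**Cost.** Wording only; no new data, and the primary keeps the full 0.05. The secondaries lose power. For a test with 80% power at 0.05, power at the first Holm step is Φ(1.960 + 0.842 − z), and the sample-size ratio needed to keep 80% is (z + 0.842)² / (1.960 + 0.842)²:

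| Secondaries | Critical z | Power | Extra participants to keep 80% |
|---|---|---|---|
| 5 | 2.576 | 59% | 49% |
| 7 | 2.690 | 54% | 59% |
| 10 | 2.807 | 50% | 70% |

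If the ten secondaries are tested whatever the primary shows, the chance of any false positive across all eleven tests is 1 − 0.95 × 0.995^10 = 9.6% if independent, and about 5% at correlation 0.9 (400,000 simulated replicates). Testing them only after a significant primary holds it at 5%, but a failed primary then rules out every secondary claim. The sponsor should choose between these and record the choice.
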